511	8 weeks. Use of anti-androgens that act peripherally to reduce hirsutism such as 5-alpha
512	reductase inhibitors (finesteride, spironolactone, flutamide) for at least 4 weeks
513	 Prior history of a malignant disease requiring chemotherapy
514	• Family or personal history of familial medullary thyroid carcinoma or multiple endocrine
515	neoplasia type 2
516	Known hypersensitivity or contraindications to use GLP1 receptor agonists
517	• Use of metformin, thiazolidinediones, GLP-1 receptor agonists, DPP-4 inhibitors, SGLT2
518	inhibitors or weight loss medications (prescription or OTC) stopped for at least 4 weeks
519	Prior use of medication to treat diabetes except gestational diabetes
520	Eating disorders (anorexia, bulimia) or gastrointestinal disorders
521	• Suspected pregnancy (documented negative serum ßhCG test), desiring pregnancy in
522	next 15 months, breastfeeding, or known pregnancy in last three months
523	• Active or prior history of substance abuse (smoke or tobacco use within past 6 months)
524	or significant intake of alcohol
525	 Previous bariatric surgery or device intervention for obesity
526	• Patient not willing to use barrier contraception during study period (unless sterilized or
527	have an IUD)
528	History of major depressive or other severe psychiatric disorders
529	Inability or refusal to comply with protocol
530	• Currently participating or having participated in an experimental drug study in previous
531	three months
532	
533	STUDY PLANS AND PROCEDURES
534	Treatment Regimen
535	Obese non-diabetic women with PCOS will be treated for 28-30 weeks with either
536	liraglutide 3 mg (LIRA 3mg) or placebo (see Figure 1-Flow of Patients through Trial).

Figure 1: Flow of Patients Through Trial

538

539 Study Assessments

540 Following written consent, all participants will undergo the following clinical, metabolic 541 and laboratory evaluations before, during and after 30 weeks of treatment. To ensure that 542 patients remain unidentified, all study subjects will be assigned an individual study identifier 543 which includes the study acronym, patient initials, and unique number. All blood samples will be 544 obtained and results identified and reported using this unique study identifier.

- 4 -

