- 618 Patients on LIRA -**S**tart injection 0.6 mg SC QD 1week, step up to 1.2 mg SC QD 1 week, to 619 1.8 mg SC QD 1 week, 2.4 mg SC QD 1week, to a max dose of 3.0 mg SQ daily.
- Patients on PL -Start injection 0.6 mg SC QD 1week, step up to 1.2 mg SC QD 1 week, to
 1.8 mg SC QD 1 week, 2.4 mg SC QD 1week, to a max dose of 3.0 mg SQ daily.

All patients will be called monthly to document the results of their home pregnancy tests and to assess compliance with the medication. Patients will receive the same counseling concerning the benefits of lifestyle modification through diet and exercise. The patients will be also encouraged to increase daily exercise (such as walking, using stairs) although this will not be formally assessed. The participants will receive further encouragement to adhere to the regime by frequent contact using follow-up phone calls. Side effects of the treatment and reason for any withdrawals from the study will be recorded.

629 C. *Week 16-18 assessment-* Patients will return to clinic for an 18-week re-evaluation of 630 clinical and anthropometric variables (height, weight, body mass index [BMI], waist and hip 631 circumference and blood pressure) and a safety assessment. A serum pregnancy test and 632 complete metabolic profile (Chem 12) and calculated eGFR will also be performed. Side effects 633 of the treatment and reason for any withdraws from the study will be recorded. Another 18 634 weeks of medication will be dispensed and 4 home pregnancy test kits following a negative 635 serum pregnancy test.

D. *Final (week 30-32) assessment-* After 28 weeks of treatment, patients will be scheduled for final evaluation. They will be instructed to stop medications 1 week prior to their laboratory assessment visit. All laboratory tests (except prolactin, TSH and hemoglobin A1C) will be repeated. All anthropometric parameters and physical including vital signs and DXA will again be performed and calculations will be repeated for post-treatment effects.

641

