During the study period, cycle control will be assessed daily by the subjects using a menstrual diary. Vaginal bleeding will be classified by the subject as either spotting (requiring at least one pad/tampon per day) or bleeding (two or more pads/ tampons per day). The effects of treatment intervention on menstrual abnormalities will be evaluated by assessing posttreatment changes in menstruation frequency over 30 weeks from the patient's menstrual cycle diary and normalized to the number of menstruations per year (52 weeks).

All side-effects will also be recorded and summarized for the 30 week-treatment period. During the whole study period, compliance to the treatment will be documented. Compliance with treatment will be checked by questioning about the side-effects and a subjective evaluation of the tolerability of the administered drug; the patients will also asked about incidental missed administrations and whether they had correctly followed the scheduled treatment. Questioning regarding the occurrence of adverse events and use of concomitant medication will take place throughout the trial.

655

656 Study Medication

657 Study Drug Storage- All investigational products (study drugs) will be stored under 658 appropriate storage conditions in a secure area according to local regulations. The investigator is responsible for ensuring that it is dispensed only to study subjects and only from official study 659 660 sites by authorized personnel, as dictated by local regulations. The investigator is responsible for 661 ensuring that the investigational product is stored under the appropriate environmental 662 conditions (temperature, light, and humidity), as noted in the product labeling. Novo Nordisk 663 will supply all investigational products. The distribution of all supplied medications is the 664 investigators' responsibility.

665 *Study Drug Records*- It is the responsibility of the investigator to ensure that the 666 unblinded study coordinator maintains a current disposition record of investigational product. 667 Records or logs must comply with applicable regulations and guidelines and should include:

- 668
- 669

672 673

674

675

- amount received and placed in storage area; amount currently in storage area
- label ID number or batch number
- amount dispensed to and returned by each subject, including unique subject
 identifiers
 - non-study disposition (e.g., lost, wasted)
 - amount destroyed at study site

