The United States Food and Drug Administration (FDA) have assigned pregnancy category X to Saxenda (3 mg liraglutide). Studies in animals or humans have demonstrated there is positive evidence of human fetal risk based on adverse reaction data from investigational or marketing experience, and the risks involved in use of the drug in pregnant women clearly outweigh potential benefits. Safer alternatives exist. If patients become pregnant during the study, all medications will be stopped and the patient will discontinue from the study.

For safety, all subjects who enter the study are evaluable. Subjects will be monitored for safety by assessment of adverse events, physical exams, vital signs and laboratory values. Continued patient safety assessment will be carried out and all adverse events documented and reported to the WHIRB. On each visit, compliance with treatment will be checked with questions about the side-effects and a subjective evaluation of the tolerability of the administered drug; the patients will also asked about incidental missed administrations.

Adverse events will be evaluated on a continuous basis while the patient is on study and until 30 days after the last dose of study drug. Patients should be followed until all treatmentrelated adverse events have recovered to baseline or are deemed irreversible by the principal investigator.

826

827 Adverse Event Procedures

An Adverse Event (AE) is defined as any new untoward medical occurrence or worsening of a preexisting medical condition in a clinical investigation subject administered an investigational (medicinal) product and that does not necessarily have a causal relationship with this treatment. An AE can therefore be any unfavorable and unintended sign (such as an abnormal laboratory finding), symptom, or disease temporally associated with the use of investigational product, whether or not considered related to the investigational product.

An Adverse Reaction (AR) is defined as any untoward and unintended responses to an investigational medicinal product related to any dose administered Thus, for an AR, a causal relationship must be at least suspected by the medical practitioner. Unexpected Adverse Reaction (UAR) is an adverse reaction, the nature or severity of which is not consistent with the applicable product information (e.g. investigator's brochure for an investigational product or summary of product characteristics for an authorized product).

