875 may not be dose related, but are unexpected, as they are not consistent with current 876 information and regarded as possibly or probably related to the trial/study product by the 877 investigator.

878 Suspected transmission of an infectious agent (e.g., pathogenic or nonpathogenic) via the study 879 drug is an SAE.

Although pregnancy, overdose, cancer, and potential drug induced liver injury (DILI) are not always serious by regulatory definition, these events must be handled as SAEs.

882 NOTE:

- 883 The following hospitalizations are not considered SAEs:
- a visit to the emergency room or other hospital department < 24 hours, that does not
 result in admission (unless considered an important medical or life-threatening event)
- 886 elective surgery, planned prior to signing consent
- 887 admissions as per protocol for a planned medical/surgical procedure
- routine health assessment requiring admission for baseline/trending of health status
 (e.g., routine colonoscopy)
- medical/surgical admission other than to remedy ill health and planned prior to entry
 into the study. Appropriate documentation is required in these cases

admission encountered for another life circumstance that carries no bearing on health
 status and requires no medical/surgical intervention (e.g., lack of housing, economic
 inadequacy, caregiver respite, family circumstances, administrative reason).

1A. Serious Adverse Event Collection and Reporting

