896 Following the subject's written consent to participate in the study, all SAEs, whether 897 related or not related to study drug, must be collected, including those thought to be associated 898 with protocol-specified procedures. All SAEs must be collected that occur during the screening 899 period and within 30 days of discontinuation of dosing. The investigator should report any SAE 900 that occurs after these time periods and that is believed to be related to study drug or protocol-901 specified procedure. All SAEs, whether they are related or not related to study drug, and 902 pregnancies must be reported to Novo Nordisk (or designee) within 24 hours. They will also be 903 reported immediately to the Woman's Hospital Foundation Institutional Review Board at (225) [contact] and Woman's Health Research Department at [contact]. SAEs must be recorded 905 on an SAE Report Form or similar form (e.g. CIOMS, MedWatch); pregnancies on a Novo Nordisk 906 approved Pregnancy Surveillance Form. Reports are to be transmitted via email or confirmed 907 facsimile (fax) transmission.

Investigators and other site personnel must inform the FDA, via a MedWatch/AdEERs form, of any serious or unexpected adverse events that occur in accordance with the reporting obligations of 21 CFR 312.32, and will concurrently forward all such reports to Novo Nordisk. A copy of the MedWatch/AdEERs report must be be transmitted via email or confirmed facsimile 912 (fax) transmission to Novo Nordisk at the time the event is reported to the FDA. It is the 913 responsibility of the investigator to compile all necessary information and ensure that the FDA 914 receives a report according to the FDA reporting requirement timelines and to ensure that these 915 reports are also submitted to Novo Nordisk at the same time.

916 When reporting to Novo Nordisk, a cover page should accompany the 917 MedWatch/AdEERs form indicating the following:

- 918 Investigator Sponsored Study (ISS)
- The investigator IND number assigned by the FDA (if applicable)
- 920 The investigator's name and address
- 921 The trial name/title and Novo Nordisk ISS reference number
- 922

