Nonserious AEs should be followed to resolution or stabilization, or reported as SAEs if they become serious. Follow-up is also required for nonserious AEs that cause interruption or discontinuation of study drug and for those present at the end of study treatment as appropriate. All identified nonserious AEs must be recorded and described on the nonserious AE page of the study record.

256 Completion of supplemental study records may be requested for AEs and/or laboratory 257 abnormalities that are reported/identified during the course of the study.

958 Laboratory Test Result Abnormalities

The following laboratory test result abnormalities should be captured on the nonserious AE study record page or SAE Report Form as appropriate:

• Any laboratory test result that is clinically significant or meets the definition of an SAE

- Any laboratory test result abnormality that required the subject to have study drug
 discontinued or interrupted
- Any laboratory test result abnormality that required the subject to receive specific corrective
 therapy.
- 966

967 It is expected that wherever possible, the clinical rather than laboratory term would be used by968 the reporting investigator (e.g., anemia versus low hemoglobin value).

969

970 Pregnancy

971 If, following initiation of the investigational product, it is subsequently discovered that a 972 study subject is pregnant or may have been pregnant at the time of investigational product 973 exposure, including during at least 6 half-lives after product administration, the investigational 974 product will be permanently discontinued.

Protocol-required procedures for study discontinuation and follow-up must be performed on
the subject unless contraindicated by pregnancy (e.g., x-ray studies). Other appropriate
pregnancy follow-up procedures should be considered if indicated.

The investigator must immediately notify Novo Nordisk (or designee) Medical Monitor of this event and complete and forward a Pregnancy Surveillance Form to Novo Nordisk (or designee) within 24 hours and in accordance with SAE reporting procedures described in Section 1A.

Follow-up information regarding the course of the pregnancy, including perinatal and neonatal outcome and, where applicable, offspring information must be reported on the Pregnancy Surveillance Form.

984 Overdose

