1021 Any significant worsening noted during interim or final physical examinations, 1022 electrocardiogram, x-ray filming, any other potential safety assessment required or not required 1023 by protocol should also be recorded as a nonserious or serious AE, as appropriate.

- 1024
- 1025 Discontinuations

1026 The reason for a subject discontinuing from the study will be recorded in the patient chart. 1027 A discontinuation occurs when an enrolled subject ceases participation in the study, regardless 1028 of the circumstances, prior to completion of the protocol. The investigator must determine the 1029 primary reason for discontinuation. Withdrawal due to adverse event will be distinguished from 1030 withdrawal due to insufficient response according to the definition of adverse event noted 1031 earlier. The final evaluation required by the protocol will be performed at the time of study discontinuation. The investigator will record the reason for study discontinuation, provide or 1032 1033 arrange for appropriate follow-up (if required) for such subjects, and document the course of the subject's condition. They will also to be reported to Woman's Hospital Foundation 1034 1035 Institutional Review Board at [contact] and Woman's Health Research Department at 1036 [contact].

1037

1038

Subjects MUST discontinue investigational product for any of the following reasons:

- Withdrawal of informed consent (subject's decision to withdraw for any reason).
- Any clinical adverse event, laboratory abnormality, or intercurrent illness, which, in
 the opinion of the investigator, indicates that continued participation in the study is
 not in the best interest of the subject.
- 1042 Pregnancy
- 1043oInstruct subjects to contact the investigator or study staff immediately if they1044suspect they might be pregnant (e.g., missed or late menstrual period) at any1045time during study participation. Institutional policy and local regulations should1046determine the frequency of study pregnancy tests for subjects enrolled in the1047study.
- 1048oThe investigator must immediately notify Novo Nordisk if a study subject1049becomes pregnant.
- Loss of ability to freely provide consent through imprisonment or involuntary incarceration for treatment of either a psychiatric or physical (e.g., infectious disease) illness.

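### Adverse events and SAEs are to be collected for 30 days after the last dose, but the last scheduled contact is about day 7 for completers and may be day 0 for women who discontinue

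*Combined protocol and SAP*

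**What the plan says.** **The window.** Under Ethical and Regulatory Requirements, adverse events are evaluated continuously "while the patient is on study and until 30 days after the last dose of study drug". Section 1A (Serious Adverse Event Collection and Reporting) requires collection of all SAEs that arise in the screening "period and within 30 days of discontinuation of dosing". Just before the note on hospitalizations, the protocol lists pregnancy with overdose, cancer and potential liver injury and says that "these events must be handled as SAEs". The separate Pregnancy section defines exposure differently, "including during at least 6 half-lives after product administration", and gives no half-life and no number of days.

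**The schedule.** Under Study Assessments, part D (the week 30-32 assessment), the instruction to completers is "They will be instructed to stop medications 1 week prior to their laboratory assessment visit". The Safety assessments section names visits at weeks 16-18 and 30-32 and none later. The monthly calls are described in part B (Treatment), where they cover home pregnancy tests and compliance. For women who leave early, the Discontinuations section says "The final evaluation required by the protocol will be performed at the time of study discontinuation". It then asks them to comply with a follow-up procedure that the protocol is said to specify, but no contact after that evaluation is described.

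**The summary.** Study Assessments says "All side-effects will also be recorded and summarized for the 30 week-treatment period".

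**The concern.** The protocol commits the site to a 30-day post-dose window and then provides no occasion to ask about most of it. If the schedule is followed as written, the trial can report that adverse events were collected to day 30, although for much of that time nobody was due to ask. A blank record would not separate a woman with no event from a woman who was not contacted.

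The Ethical and Regulatory Requirements section counts every woman who enters the study in the safety evaluation, so early discontinuers belong to the safety data, and their scheduled coverage is the shortest. If discontinuation differs between the arms, the length of active ascertainment after the last dose differs too.

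Pregnancy raises the stakes. The protocol describes the drug as pregnancy category X, says that weight loss improves ovulation, and does not permit hormonal contraception.

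**Working it through.** The plan's own figure is the 30-day window. There is no power or alpha calculation behind it, so the check is date arithmetic.

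**Inputs**
- Window after last dose: 30 days (Ethical and Regulatory Requirements; section 1A).
- Last dose to final visit, completers: 7 days (Study Assessments, part D).
- Final visit: week 30-32 (part D; Safety assessments).
- Planned treatment: women "will be treated for 28-30 weeks with either" liraglutide or placebo (Treatment Regimen).
- Final evaluation of discontinuers: at study discontinuation (Discontinuations).
- Side-effect summary: the 30-week treatment period (Study Assessments).

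**Step 1. Completers.** Days without scheduled contact = 30 − (days from last dose to final visit) = 30 − 7 = 23, and 23/30 = 76.7%.

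**Step 2. Sensitivity to the visit wording.** Part D also has the final visit scheduled after 28 weeks of treatment. If dosing ended at week 28 and the visit fell at week 30 or week 32, the gap between them would be 14 or 28 days. The uncovered part would then be 30 − 14 = 16 days (53.3%) or 30 − 28 = 2 days (6.7%). This reading conflicts with the explicit one-week instruction, and even so contact does not reach day 30.

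**Step 3. Discontinuers.** If the evaluation falls on the day of the last dose, 30 − 0 = 30 of 30 days have no scheduled contact. This is an upper bound, because the evaluation is tied to leaving the study and not to the last dose. The group is not marginal: 72 randomized less 57 planned completers is 15 women, and the stated 30% drop-out rate gives 0.30 × 72 = 21.6, about 22.

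**Step 4. Summary period against window.** Last dose one week before a week 30-32 visit is week 29 to 31. Adding 30/7 = 4.3 weeks puts the end of the window at week 33.3 to 35.3. Counting instead from the stated 28 to 30 weeks of treatment, it ends at week 32.3 to 34.3. On either count the window runs past week 30.

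**Step 5. The pregnancy exposure clause.** Its length in days = 6 × half-life in hours / 24. The half-life is not in the documents, so these values are assumptions: 12 h gives 3 days, 24 h gives 6, 28 h gives 7 and 120 h gives 30. The clause ends by the day-7 visit if the half-life is 28 h or less, and reaches 30 days only at 120 h (5 days) or more. The documents do not settle which applies.

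**Step 6. After the fix.** With a contact at day 30 or later, 0 of 30 days follow the last scheduled contact, against 23 now for completers.

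**The case against.** The strongest reply is that the protocol already obliges the site to keep following women after the last visit. Treatment-related events are followed until they recover or are judged irreversible. SAEs are followed until they resolve or stabilize. Section 2A requires follow-up of nonserious events that led to interruption or discontinuation of drug, and of those still present at the end of treatment. The Discontinuations section has the investigator arrange any follow-up needed. Later SAEs thought to be related must be reported, and spontaneous reports are accepted at any time. The women who leave because of side effects are therefore the ones with mandated follow-up.

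This stands, and it rules out calling the window unobserved. It does not close the gap, because these duties start from an event the site already knows about, or depend on the site hearing of one. None schedules a contact to find a new event.

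A woman may also still hold a home pregnancy kit after the final visit: four kits used every four weeks from week 16 or 18 run to week 32 or 34. No call to collect that result is described.

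Three stronger inferences are tempting and not supported:
- That pregnancy exposure must be followed for 30 days or more. The exposure clause is stated in half-lives, and 30 days reaches pregnancy only through its handling as an SAE. The Safety assessments section also has the week 30-32 visit confirm that the woman is not pregnant.
- That the summary excludes later events. It names the 30-week period but does not say that nothing else will be reported.
- That a single percentage of post-dose time can be given for the whole trial. That would assume every discontinuer is evaluated on her last-dose day and can be reached, but women who withdraw consent for all procedures are exempt from follow-up.

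Finally, Figure 1 and the consent form could not be read for this check and might describe a later contact. The finding is limited to the protocol text.

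**Conclusion.** The concern holds for new-onset adverse events, SAEs and pregnancies in the 30 days after the last dose. For completers, 23 of 30 days (77%) have no scheduled contact, on the protocol's explicit instruction to stop drug one week before the final visit. For discontinuers it is up to 30 of 30 days, the maximum applying if the final evaluation coincides with the last dose. In that time, new events would surface only if a woman reported them herself. The place where events in the window are to be reported is also undefined.

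This is more than missing detail, because the stated window does not match the stated schedule and summary period. It affects the completeness of the safety data and leaves the efficacy endpoints and their analysis untouched. The documents do not show that any event would be missed.

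**What to change.** Add one telephone contact at about day 30 after the last dose for every woman who took study drug, completer or not, unless she has withdrawn consent for all procedures. Use open-ended questions on adverse events and SAEs, and ask about pregnancy.

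In Study Assessments, state that adverse events are summarized from first dose to 30 days after last dose in both arms.

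Reconcile the passages on the final visit, the side-effect summary, the AE and SAE windows, the pregnancy exposure period and follow-up after discontinuation, so that they describe one schedule. Any timing of a pregnancy test after the last dose is for the sponsor to decide.

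The cost is a short amendment and at most about 72 brief calls (48 + 24 randomized, fewer after full withdrawals of consent), made by staff who already telephone monthly. The last contact moves about 30 − 7 = 23 days later for completers.
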